9.1.8. Investigator Inspections

The investigator will make available all source documents and other records for this study to Gilead's appointed study monitors, to IRBs/IECs, or to regulatory authority or health authority inspectors.

9.1.9. Protocol Compliance

The investigator is responsible for ensuring the study is conducted in accordance with the procedures and evaluations described in this protocol.

9.2. Sponsor Responsibilities

9.2.1. Protocol Modifications

Protocol modifications, except those intended to reduce immediate risk to study participants, may be made only by Gilead. The investigator must submit all protocol modifications to the IRB in accordance with local requirements and receive documented IRB approval before modifications can be implemented.

9.2.2. Study Report and Publications

A clinical study report (CSR) will be prepared. Gilead will ensure that the report meets the standards set out in the ICH Guideline for Structure and Content of CSRs (ICH E3). Note that an abbreviated report may be prepared in certain cases.

Investigators in this study may communicate, orally present, or publish in scientific journals or other scholarly media only after the following conditions have been met:

The results of the study in their entirety have been publicly disclosed by or with the consent of Gilead in an abstract, manuscript, or presentation form or the study has been completed at all study sites for at least 2 years.

The investigator will submit to Gilead any proposed publication or presentation along with the respective scientific journal or presentation forum at least 30 days before submission of the publication or presentation.

No such communication, presentation, or publication will include Gilead's confidential information (see Section 9.1.5).

The investigator will comply with Gilead's request to delete references to its confidential information (other than the study results) in any paper or presentation and agrees to withhold publication or presentation for an additional 60 days in order to obtain patent protection if deemed necessary.

9.3. Joint Investigator/Sponsor Responsibilities

9.3.1. Payment Reporting

Investigators and their study staff may be asked to provide services performed under this protocol (eg, attendance at investigator meetings). If required under the applicable statutory and regulatory requirements, Gilead will capture and disclose to Federal and State agencies any expenses paid or reimbursed for such services, including any clinical study payments, meal, travel expenses or reimbursements, consulting fees, and any other transfer of value.

9.3.2. Access to Information for Monitoring

The monitor is responsible for routine review of the CRF/eCRF at regular intervals throughout the study to verify adherence to the protocol and the completeness, consistency, and accuracy of the data being entered on them. The monitor should have access to any participant records needed to verify the entries in the CRF/eCRF. The investigator agrees to cooperate with the monitor to ensure that any problems detected through any type of monitoring (central, on site) are resolved.

9.3.3. Access to Information for Auditing or Inspections

Representatives of regulatory authorities or of Gilead may conduct inspections or audits of the clinical study. If the investigator is notified of an inspection by a regulatory authority the investigator agrees to notify the Gilead medical monitor immediately. The investigator agrees to provide to representatives of a regulatory agency or Gilead access to records, facilities, and personnel for the effective conduct of any inspection or audit.

9.3.4. Study Discontinuation

Both Gilead and the investigator reserve the right to terminate the study at any time. Should this be necessary, both parties will arrange discontinuation procedures and notify the participants, appropriate regulatory authority(ies), IRBs, and IECs. In terminating the study, Gilead and the investigator will assure that adequate consideration is given to the protection of the participants' interests.

11. APPENDICES

- Appendix 1. Investigator Signature Page
- Appendix 2. Study Procedures Table
- Appendix 3. Management of Clinical and Laboratory Adverse Events
- Appendix 4. Pregnancy Precautions, Definition for Women of Childbearing Potential, and Contraceptive Requirements
- Appendix 5. Pandemic Risk Assessment and Mitigation Plan

Appendix 2. Study Procedures Table

	Screening ^a	Day 1 ^b	Day 2	CCI	Day 8	Day 15	Every 6 weeks from Week 4 to Week 28 ±2 Days	Week 38 ±2 Days	Week 54 ±2 Days	Week 64 ±2 Days	Week 80 ±2 Days	Post Week 80 Visits ^c ±6 Days	Oral Bridging Visits ^d	30, 90, 180 Day Follow-Up ^e	Early Termination ^f
Written Informed Consent	X														
Obtain demographic information	X														
Medical History	X														
Complete Physical Examination	X	X				X	X ^g	X		X					X
Symptom-Directed Physical Examination			X		X		X ^h	X		X		X	X	X	
Vital Signs ⁱ (including weight)	X	X	X		X	X	X	X	X	X	X	X	X	X	X
12-lead ECG (supine)	X														
Height	X														
Hematology ^j , Chemistry ^k , Lipid panel ^l , Urinalysis and Urine Chemistry ^m , CD4+ Cell Count	X	X	X		X	X	X	X	X	X	X	X	X	X	X
Urine Storage Sample		X	X		X	X	X	X	X	X	X	X			X

[figure not shown]
	Screening ^a	Day 1 ^b	Day 2	CCI	Day 8	Day 15	Every 6 weeks from Week 4 to Week 28 ±2 Days	Week 38 ±2 Days	Week 54 ±2 Days	Week 66 ±2 Days	Week 80 ±2 Days	Post Week 80 Visits ^c ±6 Days	Oral Bridging Visits ^d	30, 90, 180 Day Follow-Up ^e	Early Termination ^f
Serum Pregnancy Test ^a	X														X
Serum FSH ^o	X														
Urine Pregnancy Test ^a		X	X		X	X	X	X	X	X	X	X	X	X	X
HBV, HCV Testing	X														
HIV-1 Genotyping/Phenotyping	X														
Plasma HIV-1 RNA	X	X	X		X	X	X	X	X	X	X	X	X	X	X
Plasma Storage Sample	X	X	X		X	X	X	X	X	X	X	X	X	X	X
PK Plasma Collection ^p		X	X		X	X	X	X	X	X	X	X	X		
CCI															
Oral GS-6207 Dispensation ^t		X	X		X		X	X	X	X	X	X	X		

	Screening ^a	Day 1 ^b	Day 2	CCI	Day 8	Day 15	Every 6 weeks from Week 4 to Week 28 ±2 Days	Week 38 ±2 Days	Week 54 ±2 Days	Week 64 ±2 Days	Week 80 ±2 Days	Post Week 80 Visits ^c ±6 Days	Oral Bridging Visits ^d	30, 90, 180 Day Follow-Up ^e	Early Termination ^f
Subcutaneous GS-6207 Administration ^u						X	X		X		X	X			
F/TAF Dispensation ^v		X					X	X	X	X	X	X			
TAF Dispensation ^w							X	X	X	X	X	X			
Bictegravir Dispensation ^x							X	X	X	X	X	X			
B/F/TAF Dispensation ^y		X					X	X	X	X					
Study Drug Accountability		X	X		X	X	X	X	X	X	X	X			
QoL Administration ^z		X				X	X		X		X				
Injection Site Reaction Assessment Worksheet ^{aa}						X	X		X		X				
Adverse Events/Concomitant Medications	X	X	X		X	X	X	X	X	X	X	X	X	X	X

- a Screening evaluations must be completed within 30 days prior to Day 1
- b Day 1 tests and procedures must be completed prior to administration of the dose of study drug. Participants must begin dosing on the same day as Day 1
- c Assessments will be performed post Week 80 (Week 90, Week 106, Week 116, Week 132, Week 142) and will continue to alternate between every 10 weeks and every 16 weeks with the visit window ±6 days.
- d Only applicable to participants who require oral weekly bridging if an SC injection of GS-6207 cannot be administered for any reason within the protocol visit window.
- e Participants may be required to return to the clinic for a 30, 90 and 180-Day Follow-Up Visit after Early Termination visit as noted in Section 6.4.1

- f Within 72 hours of permanently discontinuing study. Counsel participant regarding the importance of continuing a complete ARV therapy in accordance to standard of care and refer participant to an appropriate HIV treatment facility.
- g Complete physical exam is only required at Week 28
- h Symptom directed physical to be completed at Weeks 4, 10, 16, and 22, as necessary
- i Vital signs – blood pressure, pulse, respiration rate, temperature, and weight
- j Hematology: CBC with differential and platelet count
- k Chemistries: Alkaline phosphatase, AST, ALT, GGT, total bilirubin, direct and indirect bilirubin, total protein, albumin, LDH, CPK, bicarbonate, BUN, calcium, chloride, creatinine, glucose, lipase, magnesium, phosphorus, potassium, sodium, and uric acid. eGFR according to the Cockcroft-Gault formula
- l Fasting is not required for the lipid panel
- m Urinalysis and Urine Chemistry: including color & clarity, specific gravity, pH, glucose, ketones, bilirubin, urobilinogen, blood, nitrite, leukocyte esterase and microscopic (if microscopic elements are seen), urine protein, albumin, creatinine, phosphate, calcium, magnesium and uric acid
- n Women will have a serum test performed at Screening. Urine pregnancy test will only be done for women of childbearing potential. In Treatment Groups 1 and 2, urine pregnancy tests should be confirmed to be negative prior to subcutaneous GS-6207 administration. If any pregnancy test is positive, study drug should be immediately interrupted, and participant should come to the site for serum pregnancy test.
- o FSH test is required for women who are <54 years old and have stopped menstruating for ≥ 12 months but do not have documentation of ovarian hormonal failure.
- p PK collection: For Treatment Groups 1 and 2, plasma PK sampling will occur relative to dosing of GS-6207 at Days 1, 2 and 8 predose (within 30 minutes of dosing) and a single timed PK sample between 1 and 6 hours postdose. CCI [REDACTED] At Day 15 and all visits with SC GS-6207, a single predose PK sample will be collected. Starting at Week 4 and at all visits without SC GS-6207, 6207 including the Oral Bridging visits, if applicable, a single anytime PK sample will be collected. PK sampling will continue at visits past Week 80.
For Treatment Groups 3 and 4 participants, starting at Day 1, a single anytime PK sample will be collected at all study visits.
[REDACTED]
- t Treatment Group 1 and 2 oral GS-6207 lead in at Day 1, Day 2 and Day 8. Treatment Group 3 will receive oral GS-6207 lead in at Days 1 and 2 and will begin oral daily GS-6207 at Day 3.
- u Treatment Group 1 and 2 Subcutaneous administration at Day 15 and every 26 weeks
- v Treatment Group 1, 2, and 3 F/TAF once daily for 28 weeks starting at Day 1. Treatment Group 3 participants will continue F/TAF until study completion.
- w Treatment Group 1 daily oral TAF to be initiated at Week 28
- x Treatment Group 2 daily oral BIC to be initiated at Week 28
- y Treatment Group 4 daily oral B/F/TAF
- z Prior to completion of other study procedures, participants will complete HIVTSQ12, HIVDQoL, and EQ-ED-5L at Day 1 (except HIVTSQ12), Day 15 (HIVTSQ12 only), Week 4, Week 28, Week 54, Week 80. Injection Acceptability Scale and Numeric Pain Rating Scale to be completed at Day 15, Weeks 28, 54 and 80 (for Treatment Groups 1 and 2 participants only) after SC GS-6207 administration and completion of other study procedures.
- aa Provide Injection Site Reaction Assessment Worksheet and instruct the participants to measure and report injection site reactions following the administration of the subcutaneous injections (for Treatment Group 1 and 2 participants only)

Appendix 3. Management of Clinical and Laboratory Adverse Events

Appendix 4. Pregnancy Precautions, Definition for Women of Childbearing Potential, and Contraceptive Requirements

1) Definitions

a. Definition of Childbearing Potential

For the purposes of this study, a female born participant is considered a woman of childbearing potential following the initiation of puberty (Tanner stage 2) until becoming post-menopausal, unless permanently sterile or with medically documented ovarian failure. No documentation of Tanner stage will be required unless the participant is considered to be prepubescent.

Women are considered to be in a postmenopausal state when they are ≥ 54 years of age with cessation of previously occurring menses for ≥ 12 months without an alternative cause. In addition, women of < 54 years of age with amenorrhea of ≥ 12 months may also be considered postmenopausal if their follicle stimulating hormone (FSH) level is in the postmenopausal range and they are not using hormonal contraception or hormonal replacement therapy.

For the purpose of this study, permanent sterilization is hysterectomy, bilateral oophorectomy, or bilateral salpingectomy in a woman of any age. Tubal ligation is not considered permanent sterilization.

b. Definition of Male Fertility

For the purposes of this study, a male born participant is considered fertile after the initiation of puberty unless permanently sterile by bilateral orchidectomy or medical documentation.

2) Contraception Requirements for Female Born Participants

a. Study Drug Effects on Pregnancy and Hormonal Contraception

Nonclinical toxicity studies of GS-6207 have demonstrated no adverse effect on fertility or embryo-fetal development. However, there are no clinical studies of GS-6207 in pregnant women. Based on in vitro and in vivo drug-drug interaction liability assessments, a clinically significant drug-drug interaction with GS-6207 and hormonal contraceptives is not expected; an oral contraception drug-drug interaction study was not done.

No adequate and well-controlled study of F/TAF, FTC, or TAF has been conducted in pregnant women. There is an ongoing clinical study of B/F/TAF in pregnant women. Non-clinical toxicity studies of BIC, FTC, and TAF have demonstrated no adverse effect on fertility or embryo-fetal development. Neither BIC, FTC nor TAF are considered to be genotoxic. Please refer to the latest version of the investigator's brochures for additional information.

b. Contraception Requirements for Female Born Participants of Childbearing Potential

The inclusion of female born participants of childbearing potential requires using at least an acceptable effective contraceptive. They must have a negative serum pregnancy test at screening and a negative pregnancy test at the Day 1 visit prior to the dose of study drug. Pregnancy tests will be performed as defined by the study procedures in [Appendix 2](#). In the event of a delayed menstrual period (over one month between menstruations), a pregnancy test must be performed to rule out pregnancy. This is also applicable for female born participants of childbearing potential with infrequent or irregular periods.

Duration of contraception for female born participants of childbearing potential enrolled in this clinical trial should start from Screening visits until 60 days after the last dose of oral study drug or 700 days following the last dose of subcutaneous study drug, whichever is later, as applicable.

Female born participants of childbearing potential must agree to 1 of the following contraceptive methods:

- Complete abstinence from intercourse of reproductive potential. Abstinence is an acceptable method of contraception only when it is in line with the participant's preferred and usual lifestyle.

Or

- Consistent and correct use of 1 of the following methods of birth control listed below:
 - Hormonal and non-hormonal intrauterine device (IUD)
 - Bilateral tubal occlusion (upon medical assessment of surgical success)
 - Vasectomy in the male born partner (upon medical assessment of surgical success)

Or

Female born participants who initiate use of a hormonal contraceptive > 7 days after onset of menses as one of their birth control methods should use additional back-up contraception (eg, condoms) or avoid sexual intercourse for 7 days. Hormonally-based contraceptives and barrier methods permitted for use in this protocol are as follows:

- Hormonal Methods
 - Oral contraceptives (either combined or progesterone only)
 - Injectable progesterone
 - Subdermal contraceptive implant
 - Transdermal contraceptive patch
 - Contraceptive vaginal ring
- Barrier methods

- Male condom (with or without spermicide)
- Female condom (with or without spermicide)
- Diaphragm with spermicide
- Cervical cap with spermicide
- Sponge with spermicide

Inclusion of methods of contraception in this list of permitted methods does not imply that the method is approved in any country or region. Methods should only be used if locally approved.

Female born participants must also refrain from egg donation and in vitro fertilization during treatment and until the end of contraception requirement.

3) Contraception Requirements for Male Born Participants

No contraception measures are needed.

Condoms should be used for all sexual activity including oral, vaginal, and anal sexual contact to decrease the risk of transmission of HIV and other sexually transmitted diseases.

4) Unacceptable Birth Control Methods

Birth control methods that are unacceptable include periodic abstinence (eg. calendar, ovulation, symptothermal, post-ovulation methods), withdrawal (coitus interruptus), spermicides only, and lactational amenorrhea method (LAM). A female condom and a male condom should not be used together.

5) Procedures to be Followed in the Event of Pregnancy

Female born participants who are pregnant or suspect they are pregnant will be instructed to notify the investigator at any time during the study, including the protocol-defined follow-up period (Treatment Groups 1-4), and if they become pregnant within 700 days following the last dose of SC GS-6207 (Treatment Groups 1 and 2) or within 60 days following last dose of oral GS-6207. Participants who become pregnant or who suspect that they are pregnant during the study should discontinue study drug(s) immediately.

Male participants whose partner has become pregnant or suspects she is pregnant during the study, including the protocol-defined post-treatment follow-up period, must report the information to the investigator. Instructions for reporting pregnancy, partner pregnancy, and pregnancy outcome are outlined in Section 7.7.2.1.

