6.5.4. Urine Samples

Urine samples will be collected for the following laboratory analyses at every study visit, unless otherwise specified:

- Urinalysis and urine chemistry: including color & clarity, specific gravity, pH, glucose, ketones, bilirubin, urobilinogen, blood, nitrite, leukocyte esterase and microscopic (if microscopic elements are seen), urine protein, albumin, creatinine, phosphate, calcium, magnesium, and uric acid
- Urine pregnancy test for women of childbearing potential (except at Screening **CCI** visits)
 - If the test is positive, confirmatory serum test should be performed and study drug dosing should be delayed until results obtained
 - For participants in Treatment Groups 1 and 2, a confirmatory negative urine pregnancy test prior to subcutaneous GS-6207 administration must be completed.
- Urine storage for possible additional clinical testing (except at Screening, **CCI** and 30-Day, 90-Day, and 180-Day Follow-up visits, as applicable).

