6.6. Criteria for Discontinuation of Study Treatment

Study medication may be discontinued in the following instances:

- Intercurrent illness that would, in the judgment of the investigator, affect assessments of clinical status to a significant degree. Following resolution of intercurrent illness, the participant may resume study dosing at the discretion of the investigator.
- Unacceptable toxicity, or toxicity that, in the judgment of the investigator, compromises the ability to continue study-specific procedures or is considered to not be in the participant's best interest
- Lack of efficacy
- Participant request to discontinue for any reason
- Participant noncompliance
- Pregnancy during the study; refer to [Appendix 4](#).
- Discontinuation of the study at the request of Gilead, a regulatory agency or an institutional review board (IRB) or independent ethics committee (IEC)

- Participants in Treatment Groups 1 and 2 will need to have HIV-1 RNA results < 50 copies/mL at Weeks 16 and 22 to initiate treatment with a two-agent regimen at Week 28; those with values \geq 50 copies/mL will discontinue the study drug at or prior to Week 28. If data are missing at either Weeks 16 or 22 the participants discontinuation should be discussed with the medical monitor.

CCI

[REDACTED]

[REDACTED]

[REDACTED]

[REDACTED]

[REDACTED]

[REDACTED]

[REDACTED]

[REDACTED]

[REDACTED]

[REDACTED]

[REDACTED]

[REDACTED]

CCI

[REDACTED]

[REDACTED]

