6.1.1. US FDA-defined Snapshot Algorithm

The analysis window at Week 54 is defined as from Study Day 323 to Study Day 413, inclusive. All HIV-1 RNA data collected on-treatment (ie, data collected up to 1 day after the last dose date) will be used in the US FDA-defined snapshot algorithm. Virologic outcome will be defined as the following categories:

- HIV-1 RNA < 50 copies/mL: this includes subjects who have the last available on-treatment HIV-1 RNA < 50 copies/mL in the Week 54 analysis window
- HIV-1 RNA \geq 50 copies/mL: this includes subjects
 - Who have the last available on-treatment HIV-1 RNA \geq 50 copies/mL in the Week 54 analysis window, or
 - Who do not have on-treatment HIV-1 RNA data in the Week 54 analysis window and
 - Who discontinue study drug prior to or in the Week 54 analysis window due to lack of efficacy, or
 - Who discontinue study drug prior to or in the Week 54 analysis window due to reasons other than AE, death, or lack of efficacy and have the last available on-treatment HIV-1 RNA \geq 50 copies/mL
- No Virologic Data in the Week 54 analysis window: this includes subjects who do not have on-treatment HIV-1 RNA data in the Week 54 analysis window because of the following:
 - Discontinuation of study drug prior to or in the Week 54 analysis window due to AE or death (regardless of whether the last available on-treatment HIV-1 RNA < 50 copies/mL or not) or,
 - Discontinuation of study drug prior to or in the Week 54 analysis window due to reasons other than AE, death, or lack of efficacy and the last available on-treatment HIV-1 RNA < 50 copies/mL or,
 - Missing data during the window but on study drug.

The flowchart of the US FDA-defined snapshot algorithm is provided in Section 12 ([Appendix 2](#)).

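### Appendix 4 discontinues study drug on mere suspicion of pregnancy, while Section 6.5.4 and Appendix 2 hold dosing pending a serum test; the passages need reconciling

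*Protocol*

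**What the plan says.** Five places in the protocol bear on a suspected or detected pregnancy.

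- **Appendix 4, item 5 (events of pregnancy):** "Participants who become pregnant or who suspect that they are pregnant during the study should discontinue study drug(s) immediately".
- **Appendix 4, item 2b (contraception requirements):** after a delayed menstrual period, "a pregnancy test must be performed to rule out pregnancy". No stop is attached to this.
- **Section 6.5.4 (urine samples):** "If the test is positive, confirmatory serum test should be performed and study drug dosing should be delayed until results obtained".
- **Appendix 2, footnote n (repeated as footnote m of SAP Appendix 1):** "If any pregnancy test is positive, study drug should be immediately interrupted, and participant should come to the site for serum pregnancy test".
- **Section 6.6 (discontinuation criteria):** under the lead-in "Study medication may be discontinued in the following instances", one item is "Pregnancy during the study; refer to" Appendix 4.

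On the analysis side, SAP Section 3.8.1 defines a last dose date for subjects whose Study Drug Completion form records premature discontinuation. SAP Section 6.1.1 then says "All HIV-1 RNA data collected on-treatment (ie, data collected up to 1 day after the last dose date) will be used" in the snapshot algorithm.

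**The concern.** Suspicion and an unconfirmed positive test are the situations a site meets first, and for these the protocol points two ways. One route pauses dosing until a serum result. The other tells the participant to discontinue at once and says nothing of testing or resuming.

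The routes differ in consequence. Discontinuation brings an Early Termination visit within 72 hours and, depending on group and later attendance, 30-, 90- and 180-day follow-up visits (Section 6.4). A hold does none of this. Section 1.10 also names prolonged subtherapeutic GS-6207 exposure after discontinuation as a risk for resistance, so the protocol itself treats stopping as more than administrative. With about 75 centers planned and urine pregnancy tests at most visits for women of childbearing potential, sites could reasonably apply different rules to the same event. The choice can also change how the participant is classified at Week 54.

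**Working it through.** The plan gives no figure for pregnancy, so the check is mainly a comparison of texts.

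**1. The instructions side by side**

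| Situation | Appendix 4, item 5 | Elsewhere |
|---|---|---|
| Suspicion, no test yet | Discontinue immediately | Appendix 4, item 2b: test (after a delayed period); no stop stated |
| Positive test, not yet confirmed | Discontinue immediately (at least a suspicion) | Section 6.5.4: delay dosing until the serum result. Appendix 2, footnote n: interrupt, then serum test |
| Confirmed pregnancy | Discontinue immediately | Section 6.6: listed as an instance, with a pointer to Appendix 4 |

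The first two rows conflict. The third does not: Section 6.5.4 and footnote n cover only the time before the serum result, and Section 6.6 defers to Appendix 4.

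**2. Route to the Week 54 endpoint**

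- A temporary hold is not a premature discontinuation on the completion form. No last dose date is set, and the participant is classified by the last on-treatment value in the window (Days 323 to 413).
- A recorded premature discontinuation sets a last dose date. In the SC groups this comes from the oral partner drug, once an injection has been given. RNA more than 1 day later is not used.
- Section 7.7.2.1 says pregnancy itself is not an AE, so such a stop falls under other reasons. With no on-treatment sample in the window, a suppressed participant meets the no-virologic-data criterion: "reasons other than AE, death, or lack of efficacy and the last available on-treatment HIV-1 RNA < 50 copies/mL". If the last value was 50 copies/mL or more, the outcome is HIV-1 RNA ≥ 50 copies/mL. Both are non-response.
- If a suppressed on-treatment sample was taken in the window before the stop, the participant is still a responder.

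**3. How many participants**

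- Section 1.2.2.8 reports 93.4% male among 182 treated: (1 − 0.934) × 182 = 12.0. Taking this as sex at birth, it is an upper bound on those who could become pregnant. It does not allow for menopause, sterility or required contraception.
- The same section lists 22 premature discontinuations of study drug.
  - SC groups: 4 + 4 + 3 + 3 + 3 = 17 (participant decision, lost to follow-up, investigator's discretion, lack of efficacy, AE).
  - Oral GS-6207 group: 3 + 1 = 4 (lost to follow-up, participant decision).
  - B/F/TAF group: 1 (participant decision).
  - None is listed as pregnancy.

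**4. Size of one reclassification**

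- One participant is 1/25 = 4.0 points in the B/F/TAF group and 1/52 = 1.9 points in a GS-6207 group of 52.
- Illustration with the reported Week 54 counts for Group 1 (47/52) and Group 4 (23/25). It uses the standard-error form in SAP Section 6.1.2 without strata, because stratum counts are not given.
  - p1* = 47.5/53 = 0.896; p2* = 23.5/26 = 0.904.
  - SE = √(0.896 × 0.104/51 + 0.904 × 0.096/24) = 0.074.
  - Difference = 90.4% − 92.0% = −1.6 points (95% CI −16.1 to 12.8).
  - One fewer Group 1 responder: −3.5 (−18.4 to 11.3).
  - One fewer Group 4 responder: +2.4 (−13.6 to 18.4).

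A single event would move the estimate by 2 to 4 points inside an interval about 29 points wide.

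**The case against.** The strongest reply is that the passages can be read as a sequence: stop, test, confirm by serum, then act. Appendix 4 does not say the stop is permanent, whereas Sections 7.6.2 and 7.6.3 do say so where they mean it. Section 6.6 also uses the same verb over an item (intercurrent illness) that allows dosing to resume. This reply stands in part: a permanent stop is one reading of Appendix 4, not its stated meaning. But Section 6.6 gives its resumption clause to intercurrent illness only, and Appendix 4, item 5, offers neither a test nor a return. A site has to supply the sequence itself.

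Four stronger readings are tempting, and the documents do not support them.

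- **Four mutually conflicting instructions.** Delaying and interrupting are compatible, and Section 6.6 defers to Appendix 4. One mismatch remains.
- **A false alarm ends HIV treatment.** At most it ends study drug. Participants are counselled to continue complete antiretroviral therapy (Section 6.4.1), and GS-6207 exposure persists after an injection.
- **Anyone who stops cannot be a Week 54 responder.** That holds only when the stop is recorded as premature discontinuation and precedes any on-treatment sample in the window.
- **About 12 participants are affected.** Twelve is a ceiling on who could be, not a count of events. A pregnancy-related stop could have been coded under another reason, but the documents show no such case.

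It is also fair that this protocol version already reports the Week 54 results, and that the plan calls the trial underpowered for formal efficacy evaluation and non-confirmatory. New wording cannot change the conduct behind those results.

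**Conclusion.** The contradiction is real but narrow: suspected or unconfirmed pregnancy, Appendix 4, item 5, against Section 6.5.4, Appendix 2 footnote n and Appendix 4, item 2b. Its main consequence is inconsistent handling across sites, and it remains live because Groups 1 to 3 may stay on treatment after Week 80. The effect on the primary result is conditional and probably very small: up to about 12 of 182 participants at risk, no discontinuation listed as pregnancy, and 1.9 to 4.0 points for any single reclassification.

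This rests on three assumptions: that the reported male percentage reflects sex at birth; that the listed reasons do not conceal a pregnancy; and that a site following Appendix 4, item 5, literally would complete the Study Drug Completion form. The point should be corrected, but it is not a threat to the Week 54 analysis. Nothing here says which clinical instruction is right.

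**What to change.** Reconcile Section 6.5.4, Appendix 2 footnote n (with its copy in the SAP) and the two statements in Appendix 4 into one rule. State it once and cross-reference it from the other places, including Section 6.6. The rule should treat separately (a) suspicion, (b) a positive test not yet confirmed and (c) confirmed pregnancy, and should say which of these counts as premature discontinuation for Section 6.4 and for the SAP last dose date. The action attached to each is for the sponsor's clinical team.

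For data already collected, the pregnancy listing planned in SAP Section 7.6 can be used to see how any cases were handled and coded.

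Cost: protocol wording and a site memo, plus a look at a listing that is already planned.
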